3.3 Case Definitions

3.3.1 Symptomatic UTI

Symptomatic UTI is defined as an episode with one or more UTI symptoms (dysuria, urgency, frequency) prompting evaluation and treatment, with a positive urine culture. A positive urine culture is defined as $\geq 10^2$ /ml of an uropathogen in these patients.

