3.3.2 Probable UTI

Probable UTI is defined as an episode with one or more UTI symptoms (dysuria, urgency, frequency) prompting evaluation and treatment. This can occur in the absence of a MSU culture.

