6.2.1.2.2 Exclusion Criteria

1. Complicated cystitis or pyelonephritis (uncomplicated or complicated)
2. Vaginal or cervical infection, currently or within the past 30 days, with bacterial vaginosis (treated, symptomatic infection), yeast, *Trichomonas vaginalis*, *Neisseria gonorrhoeae*, *Chlamydia trachomatis* or genital Herpes simplex.

3. Symptomatic BV and/or yeast at Visit 1 (women who have Asymptomatic BV at Visit 1 may participate in the study).
4. High risk for sexually transmitted diseases and/or HIV, including: diagnosis of *N. gonorrhoeae*, *C. trachomatis* or *T. vaginalis* on two or more occasions during the previous six months;
5. History of chronic vaginal, urinary or pelvic symptoms not attributable to UTI.
6. Pregnancy or within two months of last pregnancy (all subjects must have a negative urine pregnancy test prior to randomization).
7. Lactation.
8. Antibiotic therapy (vaginal or systemic) less than three days prior to Randomization Visit (Visit 1).
9. Antifungal therapy (vaginal or systemic) less than thirty days prior to the Randomization Visit.
10. Antibiotics planned within four months (including prophylactic antibiotics).
11. Investigational drug use within 30 days or current participation in any urogenital studies.
12. Menopause.
13. Any significant disease or acute illness that in the Investigator's assessment could complicate the evaluation.
14. Known HIV infection.
15. Immunosuppressive drug within 60 days.
16. Known allergy to any component of LACTIN-V or the placebo capsule.
17. Unavailable for follow-up visits.
18. Have any social or medical condition that, in the opinion of the Investigator, would preclude provision of informed consent, make participation in the study unsafe, complicate interpretation of study outcome data, or otherwise interfere with achieving the study objectives.

Subjects who develop the following exclusion criteria while on study will discontinue study treatment, but continue to be followed for safety and efficacy endpoints whenever possible.

- Pregnancy
- Lactation
- HIV infection
- Treatment with immunosuppressive drug
- Allergy to LACTIN-V or placebo capsule

Subjects who develop any other exclusion criteria while on study will be managed at the discretion of the Investigator, in consultation with the Medical Monitor.

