10.7 Cohorts for Analyses

The intent-to-treat (ITT) cohort is defined as subjects who are randomized in the study.

The modified intent-to-treat (MITT) cohort is defined as subjects who are randomized and have received at least one dose of study product. It is a subset of the ITT cohort. It will be used for analyses of primary and secondary endpoints, baseline characteristics, trial conduct, and significant protocol deviations.

The evaluable (Eval) cohort is defined as the subset of the MITT cohort who had at least one follow-up visit assessment post-baseline (Visit 2 or later) and are not an antibiotic treatment failure at Visit 1 (defined as a requiring treatment for UTI symptoms at Visit 1). Subjects with any significant protocol deviations may be included in this cohort.

The according-to-protocol (ATP) cohort is the subset of Eval with subjects who meet all protocol specifications. Those subjects who developed exclusion criteria while on study will be excluded from this cohort.

Both Eval and ATP cohorts will be used to analyze the primary endpoints.

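### ATP, one of three unranked cohorts for the primary endpoints, can drop a woman because of the same UTI that counts as her outcome event; the effect is probably small

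*Combined protocol and SAP*

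**What the plan says.** **Cohorts (Section 10.7).** MITT is every randomized woman who received at least one dose. Of MITT the plan says "It will be used for analyses of primary and secondary endpoints". Eval is the part of MITT with a post-baseline visit and no antibiotic failure at Visit 1. ATP is the "subset of Eval with subjects who meet all protocol specifications", followed by: "Those subjects who developed exclusion criteria while on study will be excluded from this cohort". The section ends: "Both Eval and ATP cohorts will be used to analyze the primary endpoints". So three cohorts serve the primary endpoints. Neither Table 1 nor Sections 10.9.1 to 10.9.3 name a cohort.

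**Exclusion criteria (Section 6.2.1.2.2).** Criterion 1 reads "Complicated cystitis or pyelonephritis (uncomplicated or complicated". The section expects criteria to arise after entry. Five listed conditions stop study treatment; for the rest, "Subjects who develop any other exclusion criteria while on study will be managed at the discretion of the Investigator". Criterion 1 is not among the five.

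**Outcome definitions (Sections 3.3.1 and 3.3.2).** A Symptomatic UTI needs "one or more UTI symptoms (dysuria, urgency, frequency) prompting evaluation and treatment, with a positive urine culture". The broader category needs no culture: "Probable UTI is defined as an episode with one or more UTI symptoms (dysuria, urgency, frequency) prompting evaluation and treatment". Neither definition leaves out pyelonephritis or complicated cystitis, and Section 2.2.1 counts pyelonephritis within the intended indication.

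**Visit 1 antibiotic failure.** Section 4.3 defines it by a positive urine culture at that visit; Section 10.7 defines it by the need to treat urinary symptoms then.

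**The concern.** A per-protocol cohort should not lose women because they had the outcome. Read literally, the ATP rule does this for one kind of event. A pyelonephritis or complicated cystitis with dysuria, urgency or frequency that leads to evaluation and treatment is a primary-outcome event, and it is also the development of exclusion criterion 1. The woman leaves both the numerator and the denominator.

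Two things are at stake. If recurrers are removed more often than other women, the ATP recurrence rates are too low. And because no cohort is ranked, nothing in the plan says which result stands if ATP and MITT disagree. The second gap exists even if no such episode occurs.

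**Working it through.** **1. Does one episode meet both rules?**
- The ATP rule concerns criteria that develop on study and has no exception.
- The investigator's discretion in Section 6.2.1.2.2 is about managing the woman. It is not about cohort membership.
- Without dysuria, urgency or frequency the episode is not an outcome event, and the conflict does not arise. Section 5.1 has women asked about flank pain, but flank pain is not in the case definitions.
- A hospitalised episode is an SAE (7.2) and ends study treatment (8.3). Section 6.2.1.4 still asks for efficacy follow-up, so the event would be recorded. ATP loses it through the cohort rule and not through missing data.

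**2. How common could it be?** Section 2.2.2.2 (study UW/LB-001) reports 7/48 and 13/48 recurrences, 20 in all, and no pyelonephritis. The exact two-sided 95% upper limit for 0/20 is 1 − 0.025^(1/20) = 16.8% of recurrers. This covers pyelonephritis only; no rate is given for complicated cystitis.

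**3. The plan's own figure.** Section 10.4 gives 40% recurrence, a 50% reduction, 250 women and power above 80%. It states no significance level; two-sided 5% is assumed. With n = 125 per arm:
- SE under the null = √(2 × 0.30 × 0.70/125) = 0.0580
- SE under the alternative = √((0.40 × 0.60 + 0.20 × 0.80)/125) = 0.0566
- Power = Φ[(0.20 − 1.96 × 0.0580)/0.0566] = 93.7%

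The stated figure is met.

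**4. Equal removal in both arms.** Let f be the share of recurrers removed, with nobody else removed (assumptions). The ATP rate is p(1 − f)/(1 − pf).

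| f, both arms | Placebo (true 40%) | LACTIN-V (true 20%) | Risk ratio | Power |
|---|---|---|---|---|
| 0 | 40.0% | 20.0% | 0.500 | 93.7% |
| 5% | 0.38/0.98 = 38.8% | 0.19/0.99 = 19.2% | 0.495 | 92.8% |
| 16.8% | 35.7% | 17.2% | 0.483 | 90.2% |

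Five percent of recurrers at a 40% rate is 125 × 0.40 × 0.05 = 2.5 women per arm. With no true effect both ATP rates are 38.8% and type I error stays at 5.0%. Equal removal multiplies the odds in each arm by (1 − f), so the odds ratio is unchanged at 0.375; only the risk ratio and risk difference move slightly. With 276 women (Sections 4.3 and 5.1; 138 per arm) and f = 5%, power is 94.9% against 95.6%.

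**The case against.** The case for leaving this alone is substantial. Ordinary cystitis recurrences do not remove a woman: she continues product (6.3.5), and antibiotics for UTI do not end participation (6.8). MITT and Eval do not apply the rule. MITT also has the widest list of uses in Section 10.7, which suggests that it was meant as the main cohort. Any according-to-protocol cohort depends on events after randomization. All of this stands, and it limits the point to ATP. It does not supply the missing ranking: a wide list of uses does not make MITT decisive, and the same section then gives the primary endpoints to Eval and ATP as well.

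A reader might infer that the rule inflates the false-positive rate or favours LACTIN-V. That needs removal that differs by arm. With a true 40% in both arms, removing 5% of recurrers from the LACTIN-V arm only would give 38.8% against 40.0%, risk ratio 0.97 and a rejection rate of 5.4%. At 16.8% it would give 35.7% against 40.0%, risk ratio 0.89 and about 10.6%. The documents do not support such a scenario. Treatment is blinded and the applicators are described as indistinguishable (5.2, 6.2.2.1). One-arm removal would need the product to change the kind of recurrence while leaving its frequency alone, and no evidence of that is given. The direction could equally be the reverse.

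The calculation also removes recurrers only. The actual rule removes other women too, for example for yeast, BV or pregnancy. The figures therefore isolate the overlap and do not forecast the ATP result.

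**Conclusion.** The conflict is in the text. Section 10.7 has three unranked cohorts for the primary endpoints, and one of them removes a woman for an episode that can be her outcome. The size is probably small: no pyelonephritis in 20 Phase 2 recurrences, and at an assumed 5% of recurrers in both arms, about one point off each rate, no change in type I error and about one point of power. With equal removal there is no bias when the product has no effect, and the odds ratio is preserved when it has one. Material bias requires a difference between arms, which nothing in the documents indicates.

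The more important gap is the lack of a decisive cohort. These conclusions rest on the assumed removal shares, a two-sided 5% level, a two-proportion comparison, and pyelonephritis data from one small study. The two definitions of Visit 1 antibiotic failure are a separate inconsistency at baseline and add nothing to the size given here.

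**What to change.** 1. In Section 10.7, name MITT as the primary population for the primary endpoints, with Eval and ATP supportive. This is the main remedy.
2. Add to the ATP definition that an on-study UTI of any type, or its treatment, does not by itself remove a woman. Word it so that it also governs the general requirement to meet all protocol specifications.
3. Separately, reconcile Sections 4.3 and 10.7 on Visit 1 antibiotic failure, so that Eval, and ATP within it, rests on one definition.

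The second change removes the direct selection on the outcome but not all of it. Yeast or BV after UTI treatment still meets an exclusion criterion and can remove the woman, which is why ATP must stay supportive.

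The cost is wording only; no new data are needed. ATP becomes slightly larger and less strict.

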10.8 Analysis Methods

Summary statistics of frequencies, percentages, and 95% confidence intervals will be provided for categorical data. Means, standard deviations (SD), medians, and ranges (minimum, maximum) will be provided for continuous data. Chi-square test (Cochran-Mantel-Haenszel [CMH] methods), Fisher's exact test, or McNemar's test will be used for categorical variable comparisons and a t-test or rank-sum test will be used for continuous variable comparisons. Specifically, the following table lists the key variables to be analyzed by endpoint.

Table 1 **Analysis Variables and Methods**

Endpoint	Variable	Type	Statistics	Method
Primary	Percent of subjects with any Symptomatic/Probable UTI	Categorical	Frequency, Percent	95% confidence intervals
	Incidence of Symptomatic/Probable UTI	Categorical	Frequency, Percent	CMH
	Time to recurrence of first Symptomatic UTI	Numeric	Mean time to recurrence	Survival analysis, log rank test
Secondary	Change in vaginal microbiota (Nugent score)	Categorical	Frequency, Percent	Shift table (from Visit 1 to Visit 6), CMH
	Total Lactobacillus vaginal colonization	Categorical	Frequency, Percent	95% confidence interval at Visits 1-6
	Colonization with CTV-05	Categorical	Frequency, Percent	95% confidence interval at Visits 1-6

Endpoint	Variable	Type	Statistics	Method
	Total E. coli vaginal colonization	Categorical	Frequency, Percent	95% confidence interval at Visits 1-6
	Change in vaginal microbiota (DNA Amplification)	Categorical	Frequency, Percent	CMH 95% confidence interval
	H2O2, lactic acid, cytokines	Numeric	Medians, Percentiles	Wilcoxon rank-sum test
	Adverse Events, Serious Adverse Events, Symptoms, and signs of irritation on pelvic examination	Categorical	Frequency, Percent	Fisher's exact test may be used for selected AE preferred terms, symptoms or findings

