Many studies have confirmed that the critical event preceding a UTI is colonization of the vaginal introitus with gut microbiota, most commonly *E. coli* (5, 6). Women with recurrent UTI are more likely to be vaginally colonized with *E. coli* or other *Enterobacteriaceae* than women without recurrent UTI, and demonstrate prolonged periods of persistent colonization. Recent studies have verified these findings and have demonstrated a coincident loss of the normally predominant vaginal lactobacilli [10, 11, 12]. In a study in women of reproductive age, 15% of 302 women who had vaginal colonization with *L. crispatus* or *L. jensenii*, both H₂O₂ producers, were colonized with *E. coli* as compared with 27% of women who did not have these lactobacilli species present ($p = 0.01$) (7). This and other data suggest that H₂O₂-producing lactobacilli may have an important role in the maintenance of the normal vaginal ecology and in the prevention of vaginal colonization with *E. coli* and thus *E. coli*-induced UTI.

Mechanistic studies also support the ability of H₂O₂-producing lactobacilli to exclude *E. coli* vaginal colonization. Thus, Osset and colleagues showed that such lactobacilli are capable of competitive exclusion, blocking adherence of *E. coli* to vaginal epithelial cells (8). In addition, *L. crispatus* inhibits the growth of *E. coli* in both liquid and solid media through the action of H₂O₂. Finally, recent studies at the University of Washington have

shown that *L. crispatus* adheres extremely well to vaginal epithelial cells from women with recurrent UTI, suggesting it will colonize such women's vaginal epithelium (9).

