4.3 Rationale for Study Design

The study will enroll 276 pre-menopausal women currently with a symptomatic UTI who report at least one other symptomatic UTI episode treated within the past 12 months. Subjects will be randomized to receive either LACTIN-V (5×10^9 CFU/applicator) or a placebo applicator in a 1:1 ratio. The Randomization Visit (Visit 1) must occur within 3–

10 days of completing antibiotics since the vaginal microbiota is thought to be maximally disrupted at this time, thus providing *L. crispatus* CTV-05 the best chance of successful colonization.

It is not anticipated that the entry UTI episode will necessarily have fully resolved at the time of randomization (Visit 1), as mild symptoms may still be present, and the dipstick and urinalysis may still be positive or equivocal several days after completing antibiotics. However, the urine culture is anticipated to be negative at Visit 1, following completion of antibiotics; therefore, subjects with a positive urine culture at this visit will be considered an antibiotic treatment failure.

All subjects will return to clinic at 2, 4, 8, 12, and 16 weeks to assess efficacy and safety. Colonization with *L. crispatus* CTV-05 and other lactobacilli, as well as *E. coli*, will be assessed at all visits. Nugent scores will be determined at baseline and all subsequent visits to evaluate vaginal microbiota pre- and post-treatment.

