It is possible that the entry UTI episode will not be fully resolved at the time of randomization (Visit 1), as mild symptoms may still be present, and the dipstick and urinalysis may still be slightly positive or equivocal several days after completing antibiotics.

The following procedures and assessments will be performed at Visit 1:

1. Eligibility confirmed.
2. All baseline symptoms to be recorded on the CRF.
3. Urine pregnancy test performed in clinic.
4. Clean catch urinalysis and culture.
5. Vital signs.
6. Pelvic examination, to be conducted in the following order:
 - a. Examination of the external genitalia
 - b. Speculum insertion and examination of vagina, fornices and cervix with naked eye. Only water must be used to lubricate the speculum at all study visits. Other lubricants could kill *L. crispatus*.
 - c. Vaginal swab for pH, wet mount (clue cells), KOH and amine test (whiff test) performed in clinic.
 - d. Vaginal swab for gram stain Nugent score.
 - e. Vaginal swabs for culture (total lactobacilli and *E. coli*) and rep-PCR.
 - f. Swab of vaginal fluid to be stored for assessment of vaginal microbiota by DNA amplification.
 - g. Bimanual examination
7. Subject randomized.
8. First investigational applicator inserted under supervision.
9. Instructions provided to subject regarding:

- a. Study Diary
- b. Dates for initial 5 day applicator use and weekly applicator use will be marked on the Study Calendar, and staff will review with the subject how to record. If subject experiences unanticipated menses she may defer scheduled applicator use and will then record the day of actual use.

6.3.5 Visits 2 thru 5

The following procedures and assessments will be performed at follow-up Visits 2 thru 5 (unless otherwise specified):

1. All reported AEs to be recorded on the AE CRF.
2. Clean catch urine dipstick performed in clinic.
3. Urinalysis and urine culture.
4. Urine pregnancy test performed in clinic only if clinically indicated.
5. Focused physical examination, if indicated for assessment of symptoms and adverse events.
6. Pelvic examination to be conducted in the following order:
 - a. Examination of the external genitalia.
 - b. Vaginal swab for pH, wet mount (clue cells), KOH and amine test (whiff test) performed in clinic.
 - c. Vaginal swabs for culture (total lactobacilli and *E. coli*) and rep-PCR sent to laboratory
 - d. Vaginal swab for gram stain Nugent score sent to laboratory (Visit 5 only).

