10.4 Statistical Power and Sample Size Justification

Based on previous studies in this population, we estimate that 40% of women with a history of rUTI and recent treatment for a UTI will have a recurrence within the 4 month follow-up period, based on data from a recently completed rUTI study at this site (17). We plan to enroll 250 women to allow for >80% power to detect a 50% reduction in UTI incidence, also factoring in some drop-out, non-compliance and loss-to-followup, plus a cushion in case of a recurrence rate of less than 40%.

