10.9.3 Time to Recurrence of the first Symptomatic/Probable UTI episode

The time (number of days) to the first recurrence of Symptomatic/Probable UTI, as well as the time to first Symptomatic UTI, will be calculated for each subject, as measured from the date of the Randomization Visit (Visit 1) to the date of first Symptomatic/Probable UTI diagnosis post-randomization. Kaplan-Meier life-table

analysis will be used to describe the survival rates and the logrank test will be used to compare the two treatment groups.

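### The primary comparisons are valid but leave out Visit 1 vaginal E. coli, a baseline value the trial already collects, and CMH is named without a stratum: a modest gain in precision is available at almost no cost

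*Combined protocol and SAP*

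**What the plan says.** Section 10.1 sets out three main comparisons, and 10.9 gives the method for each:

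- **10.9.1, percent of women with a UTI:** number and percent by arm, with 95% confidence intervals.
- **10.9.2, episodes per woman (0, 1, 2 and so on):** a p-value by CMH methods.
- **10.9.3, time to first UTI:** Kaplan-Meier, and "the logrank test will be used to compare the two treatment groups".

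Section 10.8 lists "Chi-square test (Cochran-Mantel-Haenszel [CMH] methods" with Fisher's exact and McNemar's tests. Sections 10.8 and 10.9 name no stratum, covariate or regression model. Sections 6.2.2.1 and 10.6 describe blocked 1:1 randomization (blocks of four) with no stratification factor, so the design does not imply a stratum either.

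Section 2.1 states that "the critical event preceding a UTI is colonization of the vaginal introitus with gut microbiota", with E. coli the usual organism. The Visit 1 list in section 6.3.4 includes "Vaginal swabs for culture (total lactobacilli and" E. coli as item 6e, before randomization (item 7) and the first applicator (item 8). Section 10.3 confirms E. coli culture at Visits 1 to 6. The plan uses the result only as a secondary outcome (10.2, 10.10.3).

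**The concern.** Stratifying on a baseline factor that predicts the outcome removes variation that has nothing to do with treatment. It also protects the estimate from chance imbalance in that factor. Here the protocol's own rationale points to a candidate that is measured before treatment in every randomized woman, and the analysis ignores it.

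The CMH wording adds a smaller problem. With no stratum named, a reader cannot tell whether the test is meant to be unstratified or whether a stratum will be chosen later. A stratum chosen after outcomes are seen would weaken the result.

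At stake is some precision, which matters most if recurrence falls short of the planned 40%. Section 10.4 itself asks for a cushion against that.

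**Working it through.** **1. The plan's own power figure.** Section 10.4 says "we estimate that 40% of women with a history of rUTI and recent treatment for a UTI will have a recurrence" and "We plan to enroll 250 women to allow for >80% power to detect a 50% reduction in UTI incidence". Alpha is not stated; I take two-sided 0.05, in line with the 95% intervals. With n per arm, d = p1 − p2, V0 = p̄(1 − p̄) and V1 = p1(1 − p1) + p2(1 − p2):

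power = Φ{[d − 1.96·√(2·V0/n)] / √(V1/n)}

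For 40% v 20% and n = 125: V0 = 0.30 × 0.70 = 0.21 and V1 = 0.24 + 0.16 = 0.40. Then (0.20 − 1.96 × 0.0580)/0.0566 = 1.53, and power is 93.7%. Loss is allowed for ("also factoring in some drop-out, non-compliance and loss-to-followup") but not quantified. With 20% loss (100 per arm) power is 87.6%; with 30% it is 82.9%. The stated figure is reproduced. At 30% v 15% with no loss it is 81.4%. At 27% (the placebo rate in UW/LB-001, section 2.2.2.2) halved to 13.5%, it is 76.0%.

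**2. What CMH does without a stratum.** On a 2×2 table it equals Pearson chi-square × (N − 1)/N. For 50/125 v 25/125, Pearson is 11.90 and CMH is 11.90 × 249/250 = 11.86. It is a proper test, but it adjusts for nothing.

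**3. Gain from an E. coli stratum, percent with UTI.** Assumptions: 27% positive at Visit 1 (the higher of two background prevalences in section 2.1, from another population) and an odds ratio (OR) of 2, 3 or 5 for recurrence, with the marginal rates held fixed. V0 and V1 are replaced by their within-stratum averages. Example, OR 3 at 40% v 20%: mean risks over the two arms are 0.238 (E. coli negative) and 0.468 (positive).

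V0 = 0.73 × 0.238 × 0.762 + 0.27 × 0.468 × 0.532 = 0.1996

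This is 5.0% below 0.21, equivalent to 250 × 0.21/0.1996 = 263 women.

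| OR | Variance reduction (40% v 20%) | Equivalent N | 40% v 20%, 125/arm | 40% v 20%, 100/arm | 30% v 15%, 125/arm |
|---|---|---|---|---|---|
| 1 | 0% | 250 | 93.7% | 87.6% | 81.4% |
| 2 | 2% | 255 | 94.1% | 88.2% | 82.1% |
| 3 | 5% | 263 | 94.8% | 89.2% | 83.3% |
| 5 | 10% | 279 | 95.9% | 91.0% | 85.4% |

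Over a prevalence of 15–40%, the variance reduction is 1–2% at OR 2 and 3–6% at OR 3. In 20,000 simulated null trials at OR 3, type I error was 5.2% stratified and 4.6% unstratified.

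**4. Gain for the log-rank test.** Simulation with 250 women, 40% control recurrence, exponential times and about 15% drop-out. A second risk factor is present in 40% of women but not used in the test. The planned effect corresponds to a treatment hazard ratio (HR) of ln(0.8)/ln(0.6) = 0.44. For a weaker effect (HR 0.55) and 25% E. coli positive, 2,500 trials per row gave:

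| Prognostic HR: E. coli, other factor | Unstratified | E. coli stratum |
|---|---|---|
| 2, 2 | 68.8% | 69.8% |
| 3, 2 | 66.9% | 70.5% |
| 3, 3 | 62.5% | 66.0% |

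Across repeated runs at 25% positive, the gain is about 1–3.5 points at HR 0.44 and 1–4.5 points at HR 0.55. At 10% positive it is about 0–2.5 points. If E. coli is not prognostic, the loss is at most about 0.5 point.

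**5. Chance imbalance.** With 27% positive, the SD of the between-arm difference in prevalence is √(2 × 0.27 × 0.73/125) = 5.6 points, so a 2-SD imbalance is 11.2 points. The mean risk gap between strata is 0.144 at OR 2 and 0.335 at OR 5. Such an imbalance therefore shifts the estimated risk difference by 1.6 to 3.8 points, against a standard error of 5.7 and a planned difference of 20.

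**The case against.** The strongest case against runs as follows.

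- **The tests are valid.** Randomization protects the unadjusted comparisons. An unstratified CMH is a legitimate test for the episode-count table in 10.9.2, and because allocation was unstratified no stratum was left out by mistake. This stands. A reader might infer that the primary analysis is biased, or that CMH is misused; the documents support neither.
- **The prognostic strength is assumed.** Section 2.1 says colonization precedes UTI, but gives no recurrence risk by baseline culture. Visit 1 falls 3–10 days after antibiotics, a time section 4.3 chooses because the flora is then most disturbed. Positive cultures may be uncommon and only weakly predictive. This also stands, and it is why the gain is a range starting at zero.
- **The plan has power in hand.** At 40% v 20%, the requirement of more than 80% is met with room for about 34% loss (1 − 164/250, since 82 per arm suffice). That is so, but the margin disappears if recurrence is nearer 27–30%.

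A reader might also hope for about ten points (for example 63% to 73% at HR 0.55) by stratifying on the number of earlier UTIs as well. That needs two strong factors and a count that no section says is recorded. Inclusion criterion 4 asks for one treated episode, section 3.3.3 for one or more, and section 6.3.3 lists only a general structured history.

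**Conclusion.** The point holds as a modest improvement at almost no cost. The three primary comparisons are unadjusted, CMH has no stated stratum, and a suitable pre-dose factor is already collected. Stratifying on Visit 1 E. coli alone would add roughly 0–4.5 points of log-rank power with 250 women, if 10–25% are positive and the prognostic HR is 2–3. For the percent with UTI, the variance falls by about 2–5% at OR 2–3. The benefit is at the lower end under the plan's own assumptions and larger if recurrence or the effect is smaller. Prevalence and prognostic strength are assumptions; the documents supply neither for this population at this time point. The figures use the 250 women of section 10.4. Sections 4.3 ("The study will enroll 276 pre-menopausal women") and 5.1 give 276, which should be reconciled separately and does not change the conclusion.

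**What to change.** Before unblinding, in a dated change to 10.8 (including Table 1) and 10.9:

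- Name Visit 1 vaginal E. coli culture as the single stratification factor: positive or negative, with missing as its own category.
- **10.9.1:** report the Mantel-Haenszel stratified risk difference with its 95% confidence interval.
- **10.9.2:** stratify the CMH test by this factor.
- **10.9.3:** use the log-rank test stratified by the same factor.
- Keep the unadjusted results as supporting analyses.
- Do not add the number of earlier UTIs as a factor, since no section shows that it is recorded.

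If the sponsor prefers no adjustment, 10.8 should at least say that CMH is unstratified. Recording the choice in advance matters here because, under 6.2.2.1 and 9.1, the study statistician both holds the treatment assignments and analyzes the data.

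The cost is some SAP wording and programming, including the rule for missing cultures. No extra women, visits or assays are needed. The swab is taken at the randomization visit itself, so the factor belongs in the analysis and the allocation scheme need not change.
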